## 4. PARTICIPANT DISPOSITION

### 4.1. Participant Enrollment and Disposition

Key study dates for the first participant screened, first participant enrolled, last participant enrolled, last participant last visit for the primary efficacy endpoint, and last participant last visit for the Year 2 or Year 3 interim analysis will be provided.

A summary of participant enrollment will be provided by cohort, treatment group, and total. The number and percentage of participants enrolled in each country, investigator within a country, and overall will be summarized. For each column, the denominator for the percentage calculation will be the total number of participants analyzed for that column.

A summary of participant disposition will be provided by cohort, treatment group, and total based on all screened participants. This summary will present the number of participants screened, the number of participants who met all eligibility criteria but were not enrolled with reasons participants not enrolled, the number of participants enrolled, the number of participants enrolled but never treated (if applicable), the number of participants in the Safety Analysis Set, and the number of participants in each of the categories listed below:

#### Participant Disposition on Study Drug by Phase

- Main Phase (Up to Week 52 visit)
  - Oral lead-in before the first SC injection
    - Completed study drug
    - Prematurely discontinued study drug with reasons (if applicable)
  - After the first SC injection
    - Received Day 1 SC injection
    - Continuing study drug
    - Completed study drug
    - Prematurely discontinued study drug with reasons (if applicable)

- Extension Phase (Post Week 52 visit)
  - Treated in the extension phase
  - Completed study drug
  - Continuing study drug
  - Prematurely discontinued study drug with reasons (if applicable)

### **Participant Disposition throughout the Study**

- Continuing study
- Completed study
- Prematurely discontinued study with reasons (if applicable)

The denominator for the percentage calculation for the main phase categories and for study disposition categories will be the total number of participants in the Safety Analysis Set corresponding to that column. The denominator for the percentage calculation for the extension phase categories will be the total number of participants treated in the extension phase corresponding to that column. In addition, a flowchart will be provided to depict participant disposition on study drug.

The following by-participant listings will be provided by participant ID number in ascending order to support the above summary tables:

- Reasons for premature study drug for each phase/period or study discontinuation throughout the study
- Reasons for screen failure (will be provided by screening ID number in ascending order)

### **4.2. Study Drug Administration and Adherence**

Study drug administration and study drug dispensing information will be collected in the Study Drug Administration and Study Drug Accountability eCRFs. Number of participants receiving oral lead-in LEN and SC LEN at each protocol specified visit (Day 1, Day 2, Day 8, Day 15, Day 16, and Day 22 for oral LEN and Day 1 SC, Week 26, Week 52, Week 78, Week 104, and etc. for SC LEN) will be summarized. Number of participants receiving oral reload before the first SC injection due to missed scheduled oral dosing, and number of participants receiving oral bridging after the first SC injection will also be provided.

Study drug administration and dispensing information including lot number and kit ID (if applicable) will be listed.

The adherence to SC LEN will be assessed by adherence to the projected injection interval, which is 26 weeks (182 days) between 2 adjacent injection visits. The number of days from the projected injection visit date will be calculated for each injection visit (excluding the 1st injection visit) as the injection visit date minus the previous injection visit date minus 182 days minus oral bridging period (ie, First Dose Date of Resumed SC Injection - First Dose Date of Oral Bridging) if any occurred between these 2 adjacent injection visits. The number of days from the projected injection visit date will be classified into the following categories:

- < - 14 days
- -14 to -8 days
- -7 to -3 days
- ± 2 days
- 3 to 7 days
- 8 to 14 days
- > 14 days

The number and percentage of participants in each category will be summarized by cohort and treatment group and overall for the injection visits of interest.

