5.4. Dosing and Administration of Oral Weekly Bridging of Lenacapavir

Participants may require oral weekly bridging if an SC injection of LEN cannot be administered for any reason within the protocol visit window.

- If 26 to 28 weeks elapses since the last SC injection and if clinically appropriate to continue LEN, start oral LEN 300 mg (1 tablet) once a week at Oral Bridging visit(s) and continue weekly dosing on the same day of the week.
- If more than 28 weeks elapse since the last SC injection and if clinically appropriate to continue LEN, restart the oral lead-in at the Oral Bridging visits and continue oral weekly dosing on the same day of the week, until SC LEN is administered ([Table 2](#)).

Table 2. Dosing Schedule for Oral Weekly Bridging and Resumption of SC Lenacapavir Injection

26 to 28 weeks of elapse since the last SC injection	More than 28 weeks of elapse since the last SC injection	LEN Dose
Treatment time from oral start	Dose	—
NA	Day 1 ^a	Oral 600 mg (2 × 300 mg tablets)
NA	Day 2	Oral 600 mg (2 × 300 mg tablets)
Day 1 ^a	Day 8; continue oral weekly LEN on the same day of the week as first dose until LEN SC is administered	Oral 300 mg (1 × 300 mg tablet)
Day 8; continue oral weekly LEN on the same day of the week as first dose until LEN SC is administered	NA	Oral 300 mg (1 × 300 mg tablet) once a week
SC administration restart (within 1 week of the oral weekly 300 mg dose [as early as after Day 1 dosing])	SC administration restart (within 1 week of the oral weekly 300 mg dose [as early as after Day 8 dosing])	SC 927 mg every 6 months ^a

LEN = lenacapavir; NA = not applicable; SC = subcutaneous

^a Day 1 oral dosing and SC LEN will be administered on site, otherwise, all other oral dosing will be administered at home, but can be done on site at the investigator’s discretion.

- For oral weekly bridging, the administration of the first dose will occur on-site and up to 2 bottles of LEN will be given to the participant to take oral LEN at home; further on-site oral dosing may occur at investigator’s discretion. Up to 2 additional bottles may be given to the participant as needed upon completion of previously dispensed bottles.
- Participants may continue receiving oral weekly LEN 300 mg until they can receive their next SC LEN injection.

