### 3.8. Analysis Visit Windows

#### 3.8.1. Definition of Key Dates and Study Day

**First Dose Date** for All LEN Analysis is defined as the earliest dose date of either blinded or open-label oral LEN, as recorded on the Study Drug Administration eCRF form.

**Last Dose Date** for All LEN Analysis is defined for participants who prematurely discontinue study drug in any phase (ie, main phase or extension phase) of the study or who complete study drug as the latest dose date of either blinded or open-label oral LEN or SC LEN.

**First Dose Date** for the study is defined as the day when the first dose of blinded study drug (LEN or Placebo) or open-label oral LEN was taken, as recorded on the Study Drug Administration eCRF form.

**Last Dose Date** for the study is defined for participants who prematurely discontinue study drug in any phase of the study or who complete study drug as the latest dose date of any study drug including blinded study drug, open-label oral LEN, and SC LEN.

**First Dose Date of Oral Bridging** is defined for participants who received oral bridging of LEN as the earliest dose date of oral bridging of LEN, as recorded on the Study Drug Administration - Oral Bridging eCRF form.

**Last Dose Date of Oral Bridging** is defined for participants who received oral bridging of LEN, as the latest dose date of oral bridging of LEN before the First Dose Date of Resumed SC Injection, as recorded on the Study Drug Administration - Oral Bridging eCRF form.

**First Dose Date of Resumed SC Injection** is defined for participants who received oral bridging of LEN and resumed the SC injection, as the earliest dose date of SC LEN following the lifting of the Clinical Hold on SC LEN, as recorded on the Study Drug Administration – SC eCRF form.

**Last Study Date** is defined as the latest date of non-missing clinic visits and/or laboratory visits, and/or AE onset and end dates without any imputation, including the 30, 90, and 180-day follow-up visit dates for participants who prematurely discontinue or complete the study.

**Study Day** will be calculated from the First Dose Date, as defined separately above for All LEN Analysis and for the study, and will be derived as follows:

- For postdose study days: Assessment Date – First Dose Date + 1
- For study days prior to the first dose: Assessment Date – First Dose Date

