#### **6.2.1. US FDA-defined Snapshot Algorithm**

The analysis window at Week 104 is defined as from Study Day 688 to Study Day 778, inclusive, where Study Day is calculated from the first dose of oral LEN. Participants who have missing HIV-1 RNA at Week 104 and have completed the study before reaching the upper limit of the analysis window for Week 104 will be excluded. All HIV-1 RNA data collected on-treatment will be used in the snapshot algorithm.

HIV-1 RNA on-SC-LEN-treatment is defined as HIV-1 RNA collected up to 28 weeks from the last SC LEN, and on or prior to the first dose of oral bridging of LEN or up to 28 weeks from any resumed SC LEN after oral bridging for participants who received oral bridging of LEN.

HIV-1 RNA on-oral-LEN-treatment is defined as HIV-1 RNA collected after the First Dose Date of Oral Bridging or oral reload after the first SC LEN, and up to 7 days from the Last Dose Date of Oral Bridging for participants who discontinued from the oral bridging of LEN, or up to minimal (Last Dose Date of Oral Bridging +7, First Dose Date of Resumed SC Injection) for participants who resumed SC LEN.

For the snapshot algorithm, HIV-1 RNA on-SC-LEN-treatment will be used. If there is no such result, HIV-1 RNA on-oral-LEN-treatment will be used.

Virologic outcome will be defined as the following categories:

- HIV-1 RNA < 50 copies/mL: this includes participants who have the last available on-treatment HIV-1 RNA < 50 copies/mL in the Week 104 analysis window
- HIV-1 RNA  $\geq$  50 copies/mL: this includes participants
  - Who have the last available on-treatment HIV-1 RNA  $\geq$  50 copies/mL in the Week 104 analysis window, or
  - Who do not have on-treatment HIV-1 RNA data in the Week 104 analysis window and
    - Who discontinue study drug prior to or in the Week 104 analysis window due to lack of efficacy, or
    - Who discontinue study drug prior to or in the Week 104 analysis window due to reasons other than AE, death, or lack of efficacy and have the last available on-treatment HIV-1 RNA  $\geq$  50 copies/mL
- No Virologic Data in the Week 104 analysis window: this includes participants who do not have on-treatment HIV-1 RNA data in the Week 104 analysis window because of the following:
  - Discontinuation of study drug prior to or in the Week 104 analysis window due to AE or death (regardless of whether the last available on-treatment HIV-1 RNA < 50 copies/mL or not) or,

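### The SAP 4.2 injection-adherence formula cannot show a delay in resuming SC lenacapavir after the first oral bridging dose

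*SAP*

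**What the plan says.** SAP 4.2 measures adherence to SC lenacapavir against a projected interval, "which is 26 weeks (182 days) between 2 adjacent injection visits". The deviation for each injection after the first is "the injection visit date minus the previous injection visit date minus 182 days minus oral bridging period"; the last term reads in full "minus oral bridging period (ie, First Dose Date of Resumed SC Injection - First Dose Date of Oral Bridging) if any occurred". Deviations are then grouped into seven categories, from more than 14 days early to more than 14 days late, with a central band of ±2 days.

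SAP 3.8.1 defines the first bridging date "as the earliest dose date of oral bridging of LEN, as recorded on the Study Drug Administration - Oral Bridging eCRF form". It also defines the last bridging date, "as the latest dose date of oral bridging of LEN before the First Dose Date of Resumed SC Injection". SAP 4.2 does not use the last bridging date. SAP 6.2.1 does: for participants who resumed SC dosing, HIV-1 RNA counts as on oral treatment "up to minimal (Last Dose Date of Oral Bridging +7, First Dose Date of Resumed SC Injection".

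Protocol 5.4 has weekly bridging start 26 to 28 weeks after the last injection and continue until SC dosing restarts. Table 2 there gives the timing of the restart: "SC administration restart (within 1 week of the oral weekly 300 mg dose".

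**The concern.** The subtracted period runs from the first bridging dose to the resumed injection, whether or not oral doses were taken throughout. A participant who took one bridging dose and then nothing for months is credited with the same covered time as one who took every weekly dose.

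Lapses of this kind are foreseeable. After the first dose, bridging is taken mainly at home, and Protocol Table 3 provides for three or more consecutive missed doses. Protocol 1.6 names long spells of low drug concentration after dosing stops as a resistance risk. A reader would turn to the adherence table to see whether dosing was continuous, and for participants who missed an injection the table would not show a late return to SC dosing.

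No other planned summary quantifies dosing intervals. SAP 4.2 otherwise counts participants dosed at each visit and participants who were bridged, and Protocol 8.6.1 only lists exposure.

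**Working it through.** **Inputs.** Interval and categories: SAP 4.2. Let P be the previous injection (set to Day 0), F the first bridging dose, L the last bridging dose and R the resumed SC injection (definitions in SAP 3.8.1). R is also the injection being scored. Bridging start window: 26 to 28 weeks after the last injection, Days 182 to 196 (Protocol 5.4). The dates in the table are illustrative assumptions; the documents give no participant data.

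**1. The plan's own figure.** 26 × 7 = 182 days, as stated.

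**2. The formula.** D = (R − P) − 182 − (R − F) = F − P − 182. R drops out, and L never enters.

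**3. Start days in the protocol window.** With P = 0, D = F − 182.
- F = 182 to 184 gives 0 to 2 (category ±2): 3 start days.
- F = 185 to 189 gives 3 to 7: 5 start days.
- F = 190 to 196 gives 8 to 14: 7 start days.

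None of these 15 start days reaches the > 14 category, whatever R is. Counting early starts as well, ±2 arises for F = 180 to 184 only. A late start is still seen: F = 203 gives 21 (> 14).

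**4. A version that credits covered time only**, using the SAP 6.2.1 limit: D′ = (R − P) − 182 − (min(L + 7, R) − F). If L + 7 < R, this equals (F − P − 182) + (R − L − 7), that is, lateness in starting bridging plus uncovered time after the last dose. Otherwise D′ = D.

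| F | L | R | D (SAP 4.2) | Days beyond L + 7 | D′ |
|---|---|---|---|---|---|
| 182 | 182 | 189 | 0 (±2) | 0 | 0 (±2) |
| 182 | 182 | 272 | 0 (±2) | 83 | 83 (> 14) |
| 182 | 182 | 362 | 0 (±2) | 173 | 173 (> 14) |
| 182 | 182 | 547 | 0 (±2) | 358 | 358 (> 14) |
| 182 | 266 | 362 | 0 (±2) | 89 | 89 (> 14) |
| 182 | 357 | 362 | 0 (±2) | 0 | 0 (±2) |
| 189 | 189 | 362 | 7 (3 to 7) | 166 | 173 (> 14) |
| 196 | 196 | 362 | 14 (8 to 14) | 159 | 173 (> 14) |

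Without bridging, an injection on Day 362 scores 362 − 182 = 180 (> 14). Under SAP 4.2, one oral dose on Day 182 moves that participant to the ±2 category.

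**5. What the alternative misses.** Take bridging doses on Days 182 and 273 only, with SC on Day 280. Then min(273 + 7, 280) − 182 = 98, and D′ = 280 − 182 − 98 = 0, although 273 − 182 = 91 days (13 weeks) separate the two doses. It detects a gap at the end of bridging, not one in the middle.

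**The case against.** The strongest defence is that the clock stop is deliberate. Protocol 6.3.2 numbers visits in weeks that leave out bridging periods. The SAP metric concerns SC injections, not all lenacapavir, and resumption is tied to the lifting of a clinical hold, which neither site nor participant controlled. What is left, F − P − 182, still shows whether bridging replaced the due injection on time. This stands for dosed bridging, and step 4 leaves such participants unchanged. It does not justify crediting time after oral dosing had stopped.

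A reader might go further in four ways that the documents do not support.
- *Any bridged participant with a long gap is counted within ±2 days.* That needs a start on Days 180 to 184; other starts in the window score 3 to 14 days, and a gap before the first bridging dose is counted.
- *Lapses would be visible nowhere.* SAP 4.2 lists administration and dispensing, SAP 4.4 tabulates and lists important deviations, and SAP 4.1 reports discontinuations. These may show individual cases, though none measures gap length. The ad hoc Oral Bridging Interim Analysis (SAP 2.1.4) has been done and its tables are not in these documents, so it cannot be said that gaps went unreported.
- *SAP 4.2 contradicts 6.2.1.* It does not. The 7-day limit there decides which viral load results count as on treatment, which is a different purpose. It is relevant as a ready-made limit.
- *The cancellation always applies.* SAP 3.8.1 defines the resumed injection by reference to the clinical hold. For bridging unrelated to the hold, that date may not be the injection being scored, and the subtracted term is then unclear.

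**Conclusion.** The point holds in a limited form. For an interval that contains bridging and closes with the resumed SC injection, the deviation depends only on when bridging began. A start inside the protocol window scores 0 to 14 days late regardless of any later lapse; in the illustrations, gaps of 83 to 358 days beyond last dose plus 7 leave the score unchanged.

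The result rests on the scored injection being the resumed SC injection and on the gap falling after the first bridging dose. The documents do not say how many participants, if any, had such a gap. A gap would also mean departing from the weekly schedule in Protocol 5.4, with bridging visits due every 10 to 12 weeks as a check.

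The consequence is confined to one descriptive table with no test attached. It would be wrong to infer that the efficacy results are affected, because the snapshot analysis has its own 7-day limit on oral cover. The change is still worth making because a stated rule would otherwise score a late resumption as near schedule.

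**What to change.** In SAP 4.2, replace the subtracted period with: min(Last Dose Date of Oral Bridging + 7, date of the SC injection closing that interval) − First Dose Date of Oral Bridging, with both bridging dates taken within the interval being scored. Referring to the closing injection also removes the dependence on the clinical hold. Show bridged intervals in a separate row. Add a footnote that the measure captures only the gap between the last oral dose and SC resumption, so missed weekly doses within bridging must be read from the administration listing.

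The cost is a small change of wording and programming, with no new data. There are two downsides. The last bridging dose is often taken at home and its date may be incomplete; SAP Appendix 3, item 9 imputes it for study days on listings, and the SAP should say whether that rule extends to this table. Reported adherence may also look slightly less favourable for bridged participants.

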#### **4.3. Study Duration**

Due to long-acting feature of the study drug, study duration will be calculated for All LEN Analysis using the Safety Analysis set.

All LEN Analysis Study duration is calculated as the last study date minus the first dose date of LEN plus 1. For participants who are still on study at the time of the Year 2 or Year 3 interim analysis, the data cut date will be used to impute the last study day.

Study duration will be expressed in days and will be summarized using descriptive statistics and using the number and percentage of participants that stayed through the following applicable time periods: 1 day, 2 days, 8 days, 15 days, 43 days, 85 days, 127 days, 169 days, 197 days, etc.

#### **4.4. Protocol Deviations**

Participants who did not meet the eligibility criteria for study entry but enrolled in the study will be summarized. The summary will present the number and percentage of participants who did not meet at least 1 eligibility criterion and the number of participants who did not meet specific criteria by cohort, treatment group, and total for the Safety Analysis Set. A by-participant listing will be provided for those participants who did not meet at least 1 eligibility (inclusion or exclusion) criterion. The listing will present the eligibility criterion (or criteria if more than 1 deviation) that participants did not meet and related comments, if collected.

Protocol deviations occurring after participants entered the study are documented during routine monitoring. The number and percentage of participants with important protocol deviations and number of important protocol deviations by deviation category (eg, eligibility criteria, informed consent) will be summarized by cohort and treatment group for the Safety Analysis Set. A by-participant listing will be provided for those participants with important protocol deviation.

## 5. BASELINE CHARACTERISTICS

### 5.1. Demographics and Baseline Characteristics

Participant demographic variables (ie, age, sex at birth, gender identity, sexual orientation, race, and ethnicity) and baseline characteristics (body weight [in kg], height [in cm], body mass index [BMI; in kg/m^2]) will be summarized by cohort, treatment group, and total using descriptive statistics for continuous variables and using number and percentage of participants for categorical variables. The summary of demographic data will be provided for the Safety Analysis Set.

For Cohort 1, the Cochran-Mantel-Haenszel (CMH) test will be used to compare the 2 treatment groups (LEN vs. Placebo) for categorical data. The 2-sided Wilcoxon rank sum test will be used to compare the treatment groups (LEN vs. Placebo) for continuous data.

A by-participant demographic and baseline characteristics listing, including the informed consent date, will be provided by participant ID number in ascending order.

### 5.2. Other Baseline Characteristics

Other baseline characteristics include disease characteristics, HIV and ARV medication history (prior ARV drugs), failing regimen and resistance, and OBR and resistance at baseline:

Disease characteristics will include the following:

- HIV-1 RNA (log10 copies/mL)
- HIV-1 RNA categories (copies/mL): (a) ≤ 100,000, (b) > 100,000
- CD4 cell counts (/μL)
- CD4 cell counts categories (/uL): (a) < 50, (b) ≥ 50 to < 200, (c) ≥ 200 to < 350, (d) ≥ 350 to < 500, and (e) ≥ 500
- CD4 percentage (%)

HIV and ARV medication history will include the following:

- Number of years since HIV diagnosis
- Number of years since first started HIV treatment
- Number of prior ARV medications (see definition in Section 7.4.1.1 excluding cobicistat [COBI] and ritonavir [RTV] used as a boosting agent)

- Prior ARV medications drug class exposure: (a) nucleoside reverse transcriptase inhibitors (NRTI), (b) non-nucleoside reverse transcriptase inhibitors (NNRTI), (c) protease inhibitor (PI), (d) integrase strand-transfer inhibitor (INSTI), (e) fusion inhibitor (eg, enfuvirtide), (f) CCR5 entry inhibitor (eg, maraviroc), (g) CD4-directed post-attachment inhibitor (eg, ibalizumab), (h) attachment inhibitor (eg, fostemsavir), (i) Other, if applicable
- Number of participants with known resistance to  $\geq 2$  drugs in class

Failing regimen and resistance will include the following:

- Number of failing regimen (see definition in Section 7.4.1.2 excluding COBI and RTV used as a boosting agent)
- Failing regimen class exposure (a) NRTI, (b) NNRTI, (c) PI, (d) INSTI, (e) fusion inhibitor, (f) CCR5 entry inhibitor, (g) CD4-directed post-attachment inhibitor (eg, ibalizumab), (h) attachment inhibitor (eg, fostemsavir), (i) Other, if applicable
- OSS based on failing regimen
- GSS based on failing regimen
- PSS based on failing regimen
- Number of fully active ARV agents from failing regimen
- Use of DTG twice daily (BID) and/or DRV BID in failing regimen: (a) With DTG BID and DRV BID, (b) With DTG BID, without DRV BID, (c) Without DTG BID, with DRV BID, (d) Without DTG BID or DRV BID

OBR and resistance will include the following:

- Number of ARV medications in the baseline OBR
- Baseline OBR drug class exposure (a) NRTI, (b) NNRTI, (c) PI, (d) INSTI, (e) fusion inhibitor, (f) CCR5 entry inhibitor, (g) CD4-directed post-attachment inhibitor (eg, ibalizumab), (h) attachment inhibitor (eg, fostemsavir), (i) Other, if applicable
- OSS based on baseline OBR (as continuous variable and categorical variable: 0, 0.5, 1, 1.5, 2, > 2);
- GSS based on baseline OBR (as continuous variable and categorical variable: 0, 0.5, 1, 1.5, 2, > 2);
- PSS based on baseline OBR (as continuous variable and categorical variable: 0, 0.5, 1, 1.5, 2, > 2);

- Number of fully active ARV agents from baseline OBR
- Use of DTG and/or darunavir DRV in baseline OBR: (a) With DTG and DRV (b) With DTG, without DRV (c) Without DTG, with DRV (d) Without DTG or DRV
- Use of IMAB and/or FTR in baseline OBR: (a) With IMAB and FTR (b) With IMAB, without FTR (c) Without IMAB, with FTR (d) Without IMAB or FTR

Other baseline characteristics will be summarized by cohort and treatment group and overall using descriptive statistics for continuous variables and using number and percentage of participants for categorical variables. The summary of other baseline characteristics will be provided for the Safety Analysis Set.

For Cohort 1, the CMH test will be used to compare the 2 treatment groups for categorical data and the 2-sided Wilcoxon rank sum test will be used to compare the treatment groups for continuous data.

A by-participant listing of other baseline characteristics will be provided by participant ID number in ascending order.

